### *Exploratory subgroup analyses.*

Subgroup analyses will be conducted to understand how the intervention works. We will consider all of our predictors listed in the previous paragraph first as main effects and then as moderators to understand how predictors affect outcomes and how intervention effects possibly differ by groups defined by key predictors. For example, we will examine whether the intervention works well for meth users, but not for non-meth-users or works better for one race/ethnicity group over another. We will plot empirical summary plots (defined above) for all predictors for outcomes to understand predictor main effects on outcomes prior to subgroup analysis. Thus, for example, we will test for main effects for meth use and if present, we will attempt a multivariable model with meth-by-intervention group interactions.

### *Power Calculations.*

For each of the 11 primary outcomes, we calculated power given the Principal Investigator's (PI) estimates of probabilities of success for the 6-month outcomes for each intervention arm. These estimates were based on the existing literature and on preliminary data from the Passport to Wellness study. The PI often specified ranges, in which case we calculated power for the low end and the high end of the ranges resulting in 16 power calculations. Power for the full sample of 399 for testing  $H_0$ : *all arms have the same probability of success*, with a chi-square with 2 degrees of freedom (df) was almost always 1 to three decimal points for alpha=.05; the lowest power was .958 for probabilities of success for the three arms of (0.025, 0.075, 0.15). Some other examples of triples of probabilities we considered were (0.2, 0.6, 0.8), (0.2, 0.45, 0.55), (0.3, 0.5, 0.65). However, we expect a fair amount of loss to follow-up, so we also calculated power for 25% attrition, leaving 100 per group. Again, power is strong, but the lowest power for testing this  $H_0$  is now 86.

Second, we also considered power for comparing between the two intervention groups for testing  $H_0$ : *both intervention arms have the same probability of success*: across a wide range of baseline probabilities, we have 0.8 power at alpha=.05 to detect a difference of 0.17 at n=133, and a difference of 0.20 at n=100 (accounting for loss to follow up) in each group. Because we will be fitting longitudinal models with more data than what goes into a chi-square test, we will have increased power over this basic chi-square test on 2 df.

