### *Modeling Outcomes.*

Each outcome will be analyzed in longitudinal intention to treat using analyses of all available data from Baseline and 3-, 6-, and 12-month follow-up interviews, mobile app, and abstracted record data on utilization, as appropriate. For PrEP cascade outcomes from aim 1, the model is a logistic generalized linear mixed model (GLMM) with a random intercept for participants and a binary 0-1 outcome with 1 indicating success (screening for PrEP say) and 0 indicating a lack of success (not screening for PrEP). We generally do not expect participants to have any PrEP-related positive outcomes at baseline, and we anticipate using only follow-up data at 3, 6 and 12 months in the analysis of specific Aim 1 outcomes. The fixed effects will be a mean for every date (3, 6, 12 months) for each intervention group, for a total of 9 parameters. The first hypothesis is a test for each outcome of differences at 6 months; secondary tests are for differences at 3 months and at 12 months. If the three groups are different at a given time point, we will do pairwise comparisons among the treatments, particularly between the two intervention arms with and without PMs. Specific Aim 3 is similar, though there may be some participants with appropriate SUDs treatment prior to baseline, thus we will include the baseline observation as part of the outcome. At baseline, groups have not been affected by interventions, thus all groups will be the same, so there is one additional parameter for the baseline mean. Otherwise, the analysis is similar to Aim 1 outcome analyses.

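### For the five Aim 1 outcomes, the SAP's claim that the longitudinal model adds power over the chi-square test is not supported, and no test statistic is named for the 6-month contrast

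*SAP*

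**What the plan says.** The SAP (Power Calculations) bases power on a single-visit comparison of proportions at 6 months, with a chi-square on 2 df for equality of the three arms in a full sample of 399. It reports that power "was almost always 1 to three decimal points for alpha=.05". Its weakest case is a set of small rates, 0.025, 0.075 and 0.15, where power is given as .958. For loss to follow-up, "we also calculated power for 25% attrition, leaving 100 per group", and the minimum for the same test is then printed as 86, which I read as .86. For the two intervention arms, "we have 0.8 power at alpha=.05 to detect a difference of 0.17 at n=133, and a difference of 0.20 at n=100". The section closes with the claim at issue: "Because we will be fitting longitudinal models with more data than what goes into a chi-square test, we will have increased power".

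The model is in the SAP, Modeling Outcomes. For Aim 1 it is a logistic mixed model with a random participant intercept, fitted to the follow-up visits only. "The fixed effects will be a mean for every date (3, 6, 12 months) for each intervention group", which makes nine parameters. On the primary comparison, the SAP says: "The first hypothesis is a test for each outcome of differences at 6 months". Aim 3 adds the baseline observation with one mean common to all arms. Aim 2 uses a Poisson rate model with an offset.

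The SAP does not say whether the 6-month contrast is tested by a Wald, score or likelihood-ratio statistic. If the planned software has trouble fitting, it moves to Bayesian software, without priors or a decision rule. It gives no calculation for the claimed gain.

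**The concern.** The sentence treats more data as more power. That depends on the mean structure. If every arm has its own free mean at every visit, data from 3 and 12 months mostly inform the 3- and 12-month means. With complete data in the linear analogue, the estimated 6-month difference is exactly the difference of the 6-month arm means, whatever the within-person correlation. The logistic mixed model behaves almost the same way: the subject-specific log-odds ratio is larger than the marginal one, but its standard error grows with it. The other visits help only by partly replacing missing 6-month data.

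The sentence comes straight after the attrition figures, so a reader will take those figures as a lower bound. For Aim 1 that margin is not shown to exist.

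The unnamed test is a second, separate gap. At a planning rate of 0.025 an arm has about 2.5 to 3.3 expected successes, and the choice of statistic can then decide significance. The result feeds the rule in the SAP, Multiple Comparisons, which counts how many of the 11 outcomes reach p < 0.05.

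**Working it through.** **Inputs.** From the SAP: rates (0.025, 0.075, 0.15), 133 or 100 per arm, alpha 0.05, and the Aim 1 model above. Assumed, because the SAP gives no values: random-intercept SD of 1, 2 or 3 on the logit scale, 3- and 12-month rates equal to the 6-month rates, and a moderate-rate example of (0.3, 0.4, 0.5). Mixed models were fitted by maximum likelihood, with 800 to 1,600 simulated trials per main scenario (Monte Carlo standard error about 1 point).

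**1. The SAP's own figures.** The noncentrality is n·Σ(pᵢ − p̄)² / [p̄(1 − p̄)], with p̄ = 0.25/3 = 0.0833, Σ(pᵢ − p̄)² = 0.00792 and p̄(1 − p̄) = 0.0764. That gives 0.1036n: 13.8 at n=133 and 10.4 at n=100. The noncentral chi-square approximation gives power .924 and .830. Simulated Pearson power is .942 and .847, and the one-visit likelihood-ratio test gives .948 and .872. The simulated values are within 2 points of the stated .958 and .86. The two-arm differences also reproduce: minimum power over baseline rates is .796 (0.17, n=133) and .812 (0.20, n=100).

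**2. Aim 1 at moderate rates.** Pearson on the 6-month visit against the mixed model:

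| Setting (SD 2) | Pearson | Mixed, likelihood ratio | Mixed, Wald |
|---|---|---|---|
| 0.3/0.4/0.5, 100 per arm, complete | .759 | .754 | .746 |
| 0.3/0.4/0.5, 133 per arm, 25% missing at 6 months | .754 | .761 | .749 |

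A separate two-arm run at 0.4 v 0.6 gave Pearson .83 and likelihood ratio .82 with complete data, and .80 and .81 with 25% missing. The likelihood-ratio differences are about 1 point or less, in both directions.

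**3. Aim 1 at the SAP's lowest-power rates.**

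| Setting | SD | Pearson | Mixed, likelihood ratio | Mixed, Wald |
|---|---|---|---|---|
| 133 per arm, complete | 1 | .940 | .948 | .890 |
| 133 per arm, complete | 2 | .933 | .944 | .896 |
| 133 per arm, complete | 3 | .941 | .953 | .916 |
| 100 per arm, complete | 2 | .853 | .875 | .757 |
| 133 per arm, 25% missing at 6 months | 1 | .839 | .860 | .723 |
| 133 per arm, 25% missing at 6 months | 2 | .843 | .868 | .727 |
| 133 per arm, 25% missing at 6 months | 3 | .844 | .866 | .743 |

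The likelihood-ratio test sits 1 to 2.5 points above Pearson, but so does its one-visit form (.948 at n=133, .872 at n=100). Compared with that, the three-visit model differs by −1.2 to +0.5 points. The edge comes from the statistic, not from the extra visits.

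**4. Wald loss against Pearson.** At 133 per arm: .941 − .916 = .025 up to .940 − .890 = .050. At about 100 per arm: .853 − .757 = .096 up to .839 − .723 = .116. Exact two-arm enumeration at 0.025 v 0.15, 6-month table only, agrees: .921 − .823 = .098 at n=100 and .973 − .935 = .038 at n=133.

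**5. Zero-event arm.** 0.975¹³³ = .034 and 0.975¹⁰⁰ = .080. The estimated log-odds is then infinite and a Wald test cannot reject.

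**6. Type I error, one-visit two-arm table, both arms at 0.025 (exact).** Likelihood ratio: 9.1% at n=100 and 8.1% at n=133. Pearson, which is the score test here: 4.4% and 4.5%. At 0.05 in both arms the likelihood-ratio test rejects 6.5% and 6.0%. In the three-arm mixed model at a common rate of 0.083 and n=100 it rejects 5.1%, and Wald 3.1%. The excess is therefore confined to very sparse outcomes.

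**7. Aims 2 and 3.** For Aim 3, with an assumed common baseline rate of 0.25 and SD 2, power rises from .759 to .821 (likelihood ratio) or .811 (Wald). For Aim 2, the noncentrality for counts relative to a binary outcome runs from 21.17/27.08 = 0.78 to 31.95/24.69 = 1.29, depending on rates and overdispersion.

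**The case against.** Three points on the other side stand. First, the sentence covers all 11 outcomes, and for some it may be true: the common baseline mean in Aim 3 gave 5 to 6 points under an assumed correlation, and the Aim 2 counts may gain or lose. Second, even in Aim 1 a gain appears when within-person correlation is very high and visits are missed: a two-arm run with 133 per arm, 25% missing per visit and SD 4 gave .86 against .81. Third, nothing shows that the sample size rests on this sentence, and most of the SAP's 16 power calculations are close to 1.

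A reader might infer that the planned longitudinal test loses about 10 points of power. The documents do not support that. The loss needs a Wald test, which the SAP never names, and about 100 per arm. It is a sparse-data effect that a single visit shows as well (.712 Wald v .847 Pearson at n=100). With a likelihood-ratio test there was no material loss in any scenario run.

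A reader might also infer that a zero-event arm would certainly count as non-significant. That overlooks the Bayesian fallback, which could be invoked then, although its decision rule is not given.

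**Conclusion.** The claimed power gain is unsupported for the five Aim 1 outcomes. The 3- and 12-month data change 6-month power by about 1 point or less, at SD 2 for moderate rates and at SD 1 to 3 for the SAP's lowest rates (there against the one-visit likelihood-ratio test). This rests on assumed correlations and flat rates over time; at SD 4 with missed visits a 5-point gain is possible. It should not be read as no gain anywhere: the sentence may hold for Aim 3 and is unshown for Aim 2.

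Separately, the test is unnamed. If it were Wald, power at the lowest-power rates would fall about 3 to 5 points at 133 per arm and about 10 to 12 at about 100, and a zero-event arm (3% to 8% chance at 0.025) could not be declared significant by it. This was shown for one set of rates and is conditional on that choice. The point is a cheap correction to a stated power property, not a flaw in the design.

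**What to change.** Delete the sentence, or limit it to outcomes for which a gain has been calculated with the correlation assumption stated. Recalculate the chi-square figures for the protocol's two arms and 266 participants, and present them as approximate 6-month power for Aim 1, not as a lower bound. The current figures are for three arms and 399. They also take no account of assignment by recruitment week or month (protocol, section 6), which is a separate matter.

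Name the test. For sparse logistic outcomes, specify a score-type test of the 6-month contrast, or a likelihood-ratio test with an exact or permutation reference distribution. A permutation should re-assign recruitment periods, since these are what is randomised. Neither Wald nor an uncalibrated likelihood-ratio test is suitable there: the first loses power, and the second rejects about 8% to 9% under the null at a rate of 0.025, which would add false positives to the 3-of-11 count. The calibration figures above are for the one-visit table, so the chosen test should be checked by simulation in the mixed model. State in advance what is done when an arm has no events, including the decision rule if the Bayesian fallback is used.

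The cost is a few sentences, a little extra analysis work and a slightly less favourable power statement.

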### *Multiple Comparisons.*

We have listed 11 primary outcomes at 6 months for the three specific aims. To adjust for multiple comparisons, we propose to use a new methodology proposed in Harwood, Weiss, and Comulada (2017) (HWC17). For n=11 primary outcomes, we expect to reject on average  $0.55 = 11 * 0.05$  null hypotheses, even in the case of no difference between arms. The HWC17 methodology uses a correlated Bernoulli test of  $H_0$ : p=0.05 for n=11 outcomes that rejects the null hypothesis of no effect when 3 or more of the 11 tests are significant at p=0.05. Rejecting this null hypothesis means that the interventions are not the same, gives a type I error of .05, and accommodates correlations across outcomes. We then declare individual outcomes that produced a p-value below 0.05 as significantly different across arms as well. We will separately test outcomes at 3 months, 6 months, and 12 months using this methodology.

1. Weiss RE. *Modeling Longitudinal Data*. 2005 edition ed. Springer; 2005:454.
3. *A language and environment for statistical computing. R Foundation for Statistical Computing*. 2017:ISBN 3-900051-07-0. <http://www.r-project.org/>
4. Rubin DB. Inference and missing data. *Biometrika*. 1976:581-592.
